## **Study protocol**

**To investigate neurohistomorphological changes of the colon and rectal wall and their genesis in patients with a bowel evacuation disorder in the sense of an intestinal transit and expulsion disorder.**

### **Short title of the study:**

Neuropathological changes of the intestinal wall in patients with bowel evacuation disorder.

### **Summary:**

Constipation and defecation disorders affect about 15% of the European population and of those up to 30% of the patients over 65 years of age. For those affected, this is associated with major restrictions in quality of life and high health care costs .

The underlying causes of constipation and defecation are complex and only partially understood.

Intestinal (full wall) resections taken in clinical practice from these patients when conservative therapy has been exhausted show rarefaction of ganglion cell nests in the myenteric plexus and submucosal plexus as well as changes in cholinergic innervation [Han EC et al 2012, Bassotti G. et al 2007, Wedel T. et al 2002].

Initial histopathological investigations suggest an inflammatory genesis of this rarefaction of ganglion cell nests, which will be further characterised/investigated in the context of this study on the basis of further histopathological and serological investigations. This may lead to novel therapeutic approaches that can causally treat the symptoms of those affected.

## **Introduction:**

Intestinal transit disorders (constipation/obstipation) and/or defecation disorders (expulsion disorders) are widespread symptoms in our culture, which, depending on their severity, can become a disease. Epidemiological studies show that up to 30% of the population over the age of 65 is affected. The suffering of those affected is usually very high.

The patients are usually treated conservatively at first. The focus is on lifestyle changes, dietary adjustments and medication to support bowel movements. If the symptoms persist despite consistent conservative therapy, additional diagnostics such as laboratory tests, sonography and colonoscopy are performed. Further diagnostic steps include anal manometry, defecography and colon transit time.

In individual cases, bowel wall biopsies are taken as a further specific diagnostic tool, for example before a sacral nerve pacemaker (SNS = sacral neurostimulation) is indicated. In a study by Valli et al. it was shown that full-wall biopsies can be taken without significant risks for the patients and are very helpful for differentiated diagnosis [Valli PV et al. 2018]. In other cases, bowel resection is necessary due to mechanically induced causes of bowel dysfunction.

From 2015 onwards, the systematic neuropathological examination of whole-wall samples was performed on the bowel specimen of patients who were surgically treated in our clinic for defecation disorders. In addition, in individual cases in which no bowel resection was indicated, rectal full-wall samples were taken to confirm the diagnosis and indication for SNS and examined neuropathologically in the same way. The intestinal wall was examined for ganglion cell nests in the myenteric plexus and the submucosal plexus in order to identify the pathophysiological cause of the transport disorder.

In addition to the described rarefaction of the ganglion cell nests in the myenteric plexus and the submucosal plexus, initial results show both a change in the cholinergic innervation and changes that suggest a postinfectious reaction. Increasing evidence links gastroenteritis with chronic intestinal motility disorders [Porter CK et al. 2013, Mearin F et al. 2009], so that a *Campylobacter* or *Yersinia* infection could well be the trigger for the observed neuropathological changes. Should such an infection be diagnosed in our patient population, antibiotic treatment in the early stages of the disease could possibly prevent the neuropathological changes described.

## **The aim of the study:**

The aim of the study is to illuminate the pathomechanism of chronic intestinal emptying disorders. In addition to the identification of histopathological features on intestinal wall specimen, possible causes are to be clarified on the basis of serological investigations. If the further investigations confirm our hypothesis, novel therapeutic/preventive approaches could be generated.

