## **Type of trial, study design/methodology:**

Clinical observational study, prospective

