## **Method:**

Currently, patients found to have rarefaction of ganglion cell nests in the myenteric and submucosal plexus in whole wall specimens receive prokinetics (e.g. Resolor) or sacral neurostimulation if conservative therapy is exhausted. Those in whom this therapy fails and/or in whom bowel evacuation can be attributed to morphological changes of the bowel such as massive kinking or stenosis in the imaging programs performed (MR defecography, colon KE, CT if necessary, colon transit time measurement (Hinton test)) are candidates for bowel resection.

The following additional steps are to be taken to carry out the planned studies:

- The intestinal preparations (n=58) already taken for diagnostic purposes (rectal full-wall biopsy) or in the course of an intestinal resection on the patient's own specimen and the future specimens are to be preserved and examined in detail histopathologically and, if necessary, molecularly pathogenetically.
- In addition, EDTA blood (10ml) should be taken and stored anonymously at -20 degrees Celsius for later serological examinations for a maximum of 10 years.
- Furthermore, the clinical data will be completed with the help of a systematic questioning of the patients beyond the scope of a medical history. In addition, scores regarding their health and psychological well-being (PHQ-9), quality of life (SF-36) and their bowel habits (Wexner score and Longoscore) are collected.

The neuropathological examinations planned within the framework of this study will be carried out at the Institute for Neuropathology of the University of

Cologne, [name]. Blood samples for obtaining EDTA serum will be taken during the follow-up examination at the Evangelisches Klinikum Köln Weyertal (EVK), [name]. The EDTA serum is centrifuged at the Institute of Neuropathology of the University of Cologne, [name], stored and examined in the laboratory there.

The sample preservation of the intestinal wall for the extended neuropathological and molecular pathological processing, the clinical follow-up examinations (questioning and scores) as well as the blood samples (optional) are only taken within the framework of this study after prior information and written consent of the patient.

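### Blood storage is described as anonymous in one section and coded in another; separately, serology in cases alone cannot clarify whether infection is a cause

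*Protocol*

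**What the plan says.** **Handling of blood.** Under Method, the EDTA blood is to be "stored anonymously at -20 degrees Celsius for later serological examinations" for up to ten years. The Data protection section says that all research materials and data are pseudonymised before scientific use. The section on ethical conduct lets a patient withdraw consent at any time without giving reasons.

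**Aim.** The Summary reports first signs of an inflammatory origin of the ganglion cell loss, to be "further characterised/investigated in the context of this study on the basis of further histopathological and serological investigations". The Introduction adds that a Campylobacter or Yersinia "infection could well be the trigger for the observed neuropathological changes". The aim section then says: "possible causes are to be clarified on the basis of serological investigations. If the further investigations confirm our hypothesis", and links new therapeutic or preventive approaches to that outcome.

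**Design.** The study type is "Clinical observational study, prospective". The inclusion criterion admits only patients with severe defecation disorders who need a full-wall biopsy or resection, and the only exclusion is lack of consent. No unaffected group and no external seroprevalence are named. Tissue from 58 patients already exists ("The intestinal preparations (n=58) already taken for diagnostic purposes"), future specimens will be added, and "Blood samples for obtaining EDTA serum will be taken during the follow-up examination". Giving blood is optional.

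**The concern.** **Storage.** Anonymous and pseudonymised are different states. A pseudonymised tube carries a code that leads back to the patient's histology, questionnaire scores and history. An anonymous tube does not. A laboratory that followed the Method section to the letter would lose that link for good. What would remain is a count of positive and negative samples that could not be related to any other finding of the study.

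**Aim.** Antibodies to common enteric bacteria can show past exposure in people with no bowel disorder. A proportion seropositive among cases therefore bears on cause only when set against a proportion in comparable people without the disorder. The protocol names no such figure, yet it gives serology the task of clarifying possible causes. A reader of the results could take a raw seroprevalence in patients as evidence for an infectious trigger, and the protocol ties preventive ideas to the hypothesis being confirmed.

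**Working it through.** The protocol states no sample size target, error rate, power or seroprevalence, so there is no figure of its own to reproduce. The count of 58 is the number so far. The check is mainly a comparison of sections.

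**1. Anonymous or coded**

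| Section | What it implies for the blood |
|---|---|
| Method | Stored anonymously: no way back to the patient |
| Data protection | All materials and data pseudonymised: a code leads back to the patient |
| Ethical conduct | Consent can be withdrawn at any time; acting on this for a stored tube requires finding it |

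The Data protection wording covers all research materials, so it covers the blood. For the same tubes, both statements cannot be literally true. Only the coded version allows serology to be linked to histology, scores and clinical data, or a sample to be retrieved.

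**2. What serology in cases can estimate**

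Let p₁ be the proportion seropositive among patients and p₀ the proportion among comparable people without the disorder. The excess is p₁ − p₀, and the odds ratio is [p₁/(1 − p₁)] / [p₀/(1 − p₀)]. The design observes p₁ only. Neither quantity can be estimated at any sample size, because p₀ is neither sampled nor taken from a named source. More cases narrow the interval for p₁ and leave the gap as it is.

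*Illustration, with every rate assumed.* Suppose all 58 patients give blood and 17 are positive.

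- Observed proportion: 17/58 = 29.3%, exact 95% interval 18.1% to 42.7%.
- Count expected from background alone is 58 × p₀. The one-sided exact probability of 17 or more is P(X ≥ 17 | n = 58, p₀).

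| Assumed background p₀ | Expected positives | P(X ≥ 17) |
|---|---|---|
| 10% | 5.8 | 0.00003 |
| 20% | 11.6 | 0.059 |
| 30% | 17.4 | 0.59 |

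The same data look like strong support, borderline support or none, depending only on a rate that the protocol does not give. The protocol plans no such test. The table shows only how far the reading depends on p₀.

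**3. Time order (secondary)**

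For the 58 specimens already taken, the tissue comes first and the blood later, at follow-up. A positive result in these patients may reflect infection before or after the tissue was taken, so it cannot show that infection came before the changes. Earlier blood would not settle this either: a sample drawn on the day of the biopsy or resection would still follow the onset of disease.

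**The case against.** **The verb confirm does not belong to serology alone.** The quoted words run across two sentences. The first gives serology the possible causes. The second speaks of the further investigations together, which include histopathology and, if necessary, molecular work on the tissue. This objection stands. A reader might infer that the study cannot test its hypothesis at all, and the documents do not support that: the inflammatory origin can be examined on tissue, and the molecular work may give other evidence of infection. The point is limited to what serology is asked to do.

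**The text is already cautious.** It speaks of possible causes and says that infection could be the trigger. That is true and keeps the point modest. The sentence that has serology clarify causes remains, and the design cannot deliver it.

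**Exploratory studies need no controls, and contrasts within the cohort belong in the SAP.** Both are accepted. It would be tempting to fault the protocol for not naming a within-cohort comparison, or to call 58 patients too few for one. Neither holds: such an analysis may be in a SAP that is not shown, 58 is only a running count, and any power figure would rest on invented rates. But an analysis plan cannot supply an unaffected group that was never sampled.

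**The timing affects the whole study.** A reader might extend the time-order point to every patient. It is made here only for the 58 existing specimens, and the missing comparator is the main limitation.

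**Anonymously may just mean without a name.** This is quite possibly what was meant, and the Data protection section favours it. It does not show that samples have been or will be made unlinkable. The two sections still have to agree, because the Method section is the one that describes how the blood is stored.

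**Conclusion.** The concern holds as two separate and limited points.

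1. The Method and Data protection sections conflict on the status of the blood. If the Method wording were followed literally, serology could not be linked to the rest of the data and withdrawn samples could not be found. It may be loose wording, but the consequence for any tube stored that way is permanent.

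2. Serology is given a causal task that a cases-only cohort with no controls or reference rate cannot fulfil. It can describe seroprevalence in these patients and raise hypotheses. It cannot show that infection is more common in them than in others, or that infection caused the changes. For the 58 existing specimens it also cannot show that infection came first.

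The size of the second point cannot be computed from the protocol. The illustration rests on assumed values: 17 of 58 positive, complete blood uptake, and background rates of 10% to 30%. The conclusion itself does not depend on them.

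**What to change.** **Storage.** Reconcile the Method and Data protection sections so that the blood is stored under a code linked to the histology and clinical data. If the patient information calls the blood anonymous, align it. Cost: a code key and, if the patient information changes, a resubmission to the ethics committee.

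**Aim.** In the aim section, describe the serological part as exploratory and hypothesis-generating. State that, without unaffected controls, it cannot show that infection is more common in patients than in others or that it caused the changes. For the specimens already taken, add that blood drawn later cannot establish the order of events. Leave the inflammatory and tissue-based aims as they are, and leave any analysis within the cohort to the SAP. Cost: wording only, with no added patients, samples or procedures; the downside is a weaker stated conclusion.

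This rewording does not supply a comparator. If the sponsor wants to say that infection is more common in these patients, controls or a named reference rate would be needed, which is a larger change.

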## **Type of trial, study design/methodology:**

Clinical observational study, prospective

## **Method:**

Currently, patients found to have rarefaction of ganglion cell nests in the myenteric and submucosal plexus in whole wall specimens receive prokinetics (e.g. Resolor) or sacral neurostimulation if conservative therapy is exhausted. Those in whom this therapy fails and/or in whom bowel evacuation can be attributed to morphological changes of the bowel such as massive kinking or stenosis in the imaging programs performed (MR defecography, colon KE, CT if necessary, colon transit time measurement (Hinton test)) are candidates for bowel resection.

The following additional steps are to be taken to carry out the planned studies:

- The intestinal preparations (n=58) already taken for diagnostic purposes (rectal full-wall biopsy) or in the course of an intestinal resection on the patient's own specimen and the future specimens are to be preserved and examined in detail histopathologically and, if necessary, molecularly pathogenetically.
- In addition, EDTA blood (10ml) should be taken and stored anonymously at -20 degrees Celsius for later serological examinations for a maximum of 10 years.
- Furthermore, the clinical data will be completed with the help of a systematic questioning of the patients beyond the scope of a medical history. In addition, scores regarding their health and psychological well-being (PHQ-9), quality of life (SF-36) and their bowel habits (Wexner score and Longoscore) are collected.

The neuropathological examinations planned within the framework of this study will be carried out at the Institute for Neuropathology of the University of

Cologne, [name]. Blood samples for obtaining EDTA serum will be taken during the follow-up examination at the Evangelisches Klinikum Köln Weyertal (EVK), [name]. The EDTA serum is centrifuged at the Institute of Neuropathology of the University of Cologne, [name], stored and examined in the laboratory there.

The sample preservation of the intestinal wall for the extended neuropathological and molecular pathological processing, the clinical follow-up examinations (questioning and scores) as well as the blood samples (optional) are only taken within the framework of this study after prior information and written consent of the patient.

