### **Data protection:**

The provisions of the data protection laws are observed. It is ensured that all research materials and data are adequately pseudo-anonymized in accordance with data protection regulations prior to scientific utilization. People who do not consent to the disclosure will not be included in the study.

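### The Method section has the blood for serology stored anonymously, while the Data protection section has all research materials pseudo-anonymized; the two should be aligned so that serology can be matched to tissue.

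*Protocol*

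**What the plan says.** The Protocol describes the identification of the blood samples in two places.

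- Method, list of additional steps: "EDTA blood (10ml) should be taken and stored anonymously at -20 degrees Celsius for later serological examinations for a maximum of 10 years".
- Data protection: it is ensured that "all research materials and data are adequately pseudo-anonymized in accordance with data protection regulations prior to scientific utilization". Blood is not excepted.

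The purpose of the serology appears in four places.

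- The title asks for "neurohistomorphological changes of the colon and rectal wall and their genesis in patients with a bowel evacuation disorder".
- The Summary suspects an inflammatory origin of the loss of ganglion cell nests, "which will be further characterised/investigated in the context of this study on the basis of further histopathological and serological investigations".
- The Introduction considers that a *Campylobacter* or *Yersinia* "infection could well be the trigger for the observed neuropathological changes".
- The aim of the study states that "possible causes are to be clarified on the basis of serological investigations".

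On timing, Method refers to "The intestinal preparations (n=58) already taken for diagnostic purposes" or during a resection, and adds: "Blood samples for obtaining EDTA serum will be taken during the follow-up examination". Method also makes the blood sample optional and places both the tissue and the serum examinations at the same neuropathology institute. The section on ethical conduct lets a patient withdraw consent at any time without giving reasons.

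**The concern.** Anonymous and pseudonymised storage are different things. An anonymous sample keeps no route back to the patient, whereas a pseudonymised one keeps a coded route. The Protocol assigns the first to the blood in one section and, in effect, the second in another.

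The difference bears on the scientific question. Asking whether infection or inflammation lies behind the tissue changes is most naturally answered by setting a patient's serology beside that patient's histology and clinical scores. All included patients have a severe defecation disorder and the Protocol describes no control group, so a comparison inside the cohort is the obvious one to make. Blood stored with no link would put that comparison at risk, and a link not kept at storage cannot be restored. The study is ongoing, so samples may be stored before the wording is settled.

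**Working it through.** No arithmetic applies: the Protocol states no figure on which this point depends. The check is a comparison of the texts.

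1. **Do both statements cover the same samples?** Yes. Blood kept for serology is a research material, and the Data protection section speaks of all such materials.

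2. **Does the timing reconcile them?** The Data protection section fixes the state before scientific use, and Method fixes the state at storage. Storage comes first. A code can be removed from a sample later, but a patient code cannot be added to a sample stored without one. The Data protection requirement can therefore be met for the blood only if a code is kept throughout storage, which *anonymously*, read literally, excludes.

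3. **Is a code described anywhere?** Not in the text shown. No section mentions a code, a key or a key holder joining blood, tissue and questionnaire data.

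4. **Would blood and tissue be joined without one?** Not by arriving together. For the 58 specimens already taken, the blood is drawn later, at the follow-up examination at the hospital, and is then centrifuged, stored and examined at the neuropathology institute. Some identifier is needed to match the two.

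5. **Does the aim need the match?** The title, Summary, Introduction and aim all point to explaining tissue changes through serology. None of them lays down a patient-by-patient analysis, so the need is inferred from the aim and is not a stated rule.

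6. **Is there another consequence?** Yes. If a patient withdrew consent, an anonymously stored sample could not be located.

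7. **How many patients are involved?** At most 58 so far (Method; Patient numbers), fewer because blood is optional, plus future patients. The number who have given blood is not stated.

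**The case against.** The strongest reply is that the Data protection section already settles the matter. It is the dedicated section, it covers all materials, and it can be satisfied only by keeping a code, so a reader applying the whole Protocol would keep one. The vocabulary is also loose: *pseudo-anonymized* is not defined, and *anonymously* may be a casual word for coded. The consent pages, not shown here, may describe the coding. Much of this stands. It makes coded storage the likely intent and keeps the point a matter of wording. It does not remove the conflict, because staff handling the blood would look to Method, and Method says something else.

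A reader might go further and infer that no serology result could be paired with tissue, so that only an overall seropositive share would remain. The Protocol does not support that. Anonymity concerns the link to the person. An unlinked sample could still carry a histology category on its label, or share a sample number with the tissue while no key to the patient is kept. No such labelling is described, but none is excluded. Nor does the Protocol define a seropositive outcome from which a loss could be calculated. What can be said is that matching would not be reliable, not that it would be impossible.

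**Conclusion.** The inconsistency is real and should be corrected. Method and Data protection give different instructions for the same blood samples, and the order of storage and use does not reconcile them. Followed literally, Method would prevent reliable later matching of serology to the same patient's histology and scores, would limit the aim of clarifying the genesis of the tissue changes, and would leave a sample untraceable on withdrawal.

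The size cannot be put in figures. If coded storage is what is meant, nothing is lost and only the wording is wrong. The conclusion rests on two assumptions: that *anonymously* carries its literal sense, and that the causal aim calls for linking serology to tissue within patients, which the Protocol implies but does not specify. Confidence is medium.

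**What to change.** In Method, replace the words *stored anonymously* with: stored pseudonymised under the study code also used for the tissue and clinical data. This agrees with the Data protection section and is practicable, since tissue and serum are examined at the same institute.

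The cost is small. A key must be kept securely for as long as samples are stored, up to 10 years, and coded samples protect privacy less than anonymous ones. The consent wording, which is not shown, must be checked for consistency. If it has to change, it must go back to the ethics committee before use, as the section on ethical conduct requires. Blood already given under a promise of anonymity, if there was one, may have to stay unlinked.

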**Patient numbers:**

58 so far (ongoing study)

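### Does the mention of EDTA serum leave the study without a usable blood sample for its serology?

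*Protocol*

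**What the plan says.** The blood sample is described in two places in the protocol's Method section.

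- The bullet list of additional steps says: "EDTA blood (10ml) should be taken and stored anonymously at -20 degrees Celsius for later serological examinations for a maximum of 10 years". It names no place and no separation step.
- A later paragraph assigns the work to institutions. It says: "Blood samples for obtaining EDTA serum will be taken during the follow-up examination", at the clinic in Cologne. It continues: "The EDTA serum is centrifuged at the Institute of Neuropathology of the University of Cologne", and the material is then "stored and examined in the laboratory there".

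The closing paragraph of the same section makes blood sampling optional and subject to written consent. The section on the aim of the study gives the purpose of the serology: "possible causes are to be clarified on the basis of serological investigations".

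**The concern.** Serum is the fluid left after blood has clotted. EDTA stops clotting, so an EDTA tube yields plasma when spun, and the term EDTA serum contradicts itself. It appears twice, and the protocol mentions neither plasma, nor a serum tube, nor a clotting step.

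The stored material also seems to differ: blood in the bullet, a centrifuged fluid in the later paragraph. If someone acted on "EDTA blood (10ml) should be taken and stored anonymously at -20 degrees Celsius" alone, whole blood would be frozen. Freezing bursts the red cells, and clean plasma cannot be recovered afterwards.

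The stake would be the serological part of the aim. If some patients had haemolysed blood and others plasma, or if the assay's cut-off had been set for serum, past infection could be misclassified. Because samples may be kept for up to 10 years before testing, such an error might be found only when it could no longer be repaired.

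**Working it through.** No arithmetic applies, and the protocol gives no figure to reproduce on this point. The check is to set the two descriptions side by side and see where they conflict.

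| Item | Bullet on the blood sample | Later paragraph on institutions |
|---|---|---|
| Tube and volume | EDTA, 10 ml | EDTA, volume not given |
| Place of draw | not given | the clinic, at follow-up |
| Separation | not given | centrifuged at the neuropathology institute |
| Place of storage | not given | the same institute |
| Temperature and limit | -20 degrees Celsius, at most 10 years | not given |
| Name of the material | blood | EDTA serum |

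**Step 1: conflict or complement.** In four of the six rows only one description speaks. On the tube the two agree. They differ only in the name of the material. Otherwise the bullet gives specimen, volume, temperature and duration, and the paragraph gives place and order. The paragraph lists centrifugation first, then storage, then examination, which puts separation before freezing.

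**Step 2: what the chain produces.** EDTA blood that is centrifuged and then stored is EDTA plasma. The word serum is wrong; the material is well defined.

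**Step 3: whether plasma defeats the purpose.** The Introduction names *Campylobacter* and *Yersinia* as possible triggers. The protocol names no test, analyte, kit or cut-off for them. That no serum results is true, but it is a defect only if the assay needs serum, and the document does not say so.

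**Step 4: whether the material could differ between patients.** One clinic draws the blood and one laboratory processes and tests it, so there are no sites to diverge. The 58 mentioned in the Method section counts intestinal preparations, not blood samples. Blood is listed among the additional steps, with the same procedure for existing and future patients, and nothing says that any blood is already stored. Confounding of sample type with calendar time therefore has no basis in the text.

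**Step 5: how much rests on the serology.** The Summary assigns the question of an inflammatory origin to histopathology and serology together, and the Method section allows molecular work on the tissue. Serology is one strand of the enquiry into cause, on an optional sample.

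**The case for a change.** The strongest case for acting is this. Specimen type and processing order belong in a protocol and cannot be left to an analysis plan. The protocol does not omit them; it words them wrongly, and does so twice. Blood is drawn at one institution and spun at another, and no sentence states outright that separation comes before the -20 degrees step; that order is inferred from the sequence of verbs. Reading serum as plasma does not remove this ambiguity. The samples cannot be replaced, recruitment is ongoing, and two reworded sentences would settle it.

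Part of this stands. The term is wrong, the bullet leaves out the separation step, and a tidier text would name the material once. What does not stand is the step from there to a damaged result. Freezing whole blood requires reading the bullet while ignoring the paragraph that describes the handling. Misclassification requires a serum-only assay that the protocol does not specify. Differences between patients require several sites or a change of procedure, and neither is described. That correction is cheap does not show that leaving the wording alone does harm.

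**Conclusion.** The concern is right about the wording and does not hold as a flaw in the plan. What remains is a misnomer, possibly loose or translated wording for plasma, and a missing pre-analytical detail that a laboratory procedure would normally hold. Its reach is at most one optional 10 ml sample per consenting patient. Its effect on any stated statistical figure is nil, because the protocol gives none that depends on it. The size of any assay error cannot be derived from the document.

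This rests on two assumptions: that the laboratory reads the Method section as a whole and separates before freezing, and that the assay eventually chosen is suitable for the material held. Both are ordinary laboratory practice, and nothing in the protocol points the other way. The wording can be tidied whenever the text is next revised; no change to the design or the analysis is called for.
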